5.3 Schematic diagram

A full visit schedule is presented in [Table 5–3](#).

Table 5–3: Full visit schedule

First year follow-up		
Month (Week)	Visit	Type of visit
-2 to -21 days	V0	SV ^a
M0 (W0)	V1	EV
M1 (W4)	V2 ^c	MEV ^b
M2 (W8)	V3 ^c	FEV
M3 (W12)	V4	MEV ^b
M4 (W16)	-	-
M5 (W20)	-	-
M6 (W24)	V5	FEV
M7 (W28)	-	-
M8 (W32)	-	-
M9 (W36)	V6	MEV ^b
M10 (W40)	-	-
M11 (W44)	-	-
M12 (W48)	V7	YEV
Second year follow-up ^c		
Month	Visit	Type of visit
M15 (W60)	V8	MEV ^b
M18 (W72)	V9	FEV
M21 (W84)	V10	MEV ^b
M24 (W96)	V11	YEV

EV=Entry Visit; FEV=Full Evaluation Visit; M=month; MEV=Minimal Evaluation Visit; SV=Screening Visit; V=Visit; W=Week; YEV=Yearly Evaluation Visit

Note: A dash (-) denotes that no visit is scheduled in that month.

^a For subjects directly enrolled into EP0085 in Japan only.

^b Laboratory safety assessments will not be performed at MEV. Only liver function tests will be performed at MEV in the first year (V4 and V6).

^c Subsequent years will follow the same visit schedule.

5.4 Rationale for study design and selection of dose

Directly enrolled subjects and subjects from EP0083 will be started on a BRV dose of 100mg/day (2 equally divided doses administered twice daily) at study entry and should be maintained at this dose for at least 2 weeks, unless the subject is not able to tolerate treatment. Subjects who entered from N01379 can enter EP0085 at a dose up to 200mg/day. The BRV 50 to 200mg/day is approved as the effective dose of BRV for adults in EU/US without titration. The BRV dose can be adjusted based on the individual subject's seizure control and tolerability between 50mg/day and 200mg/day during the study and must always be administered in equal morning and evening doses except the last week of down-titration. Of note, decreasing the dose should not exceed 50mg/day. Study medication in the last week of down-titration is given only in the morning.

In Phase 2/3 studies for partial seizures with BRV doses up to 200mg/day, BRV had a low dropout rate and was generally well tolerated. The most frequently reported TEAEs were headache, somnolence, dizziness, and fatigue. The starting dose of BRV 100mg/day was selected from N01358 efficacy results that were numerically similar between 100 and 200mg/day, and the starting dose in US and EU labeling. The BRV dose can be adjusted based on the individual subject's seizure control and/or tolerability after the first 2 weeks, up to a maximum dose of BRV 200mg/day.

6 SELECTION AND WITHDRAWAL OF SUBJECTS

6.1 Eligibility criteria in Japan

6.1.1 Inclusion criteria for all subjects

To be eligible to participate in this study, all of the following criteria must be met for all subjects in Japan:

1. An IRB/IEC approved written informed consent signed and dated by the subject or by parent(s) or legally representative. The consent form or a specific assent form, where required, will be signed and dated by minors.
2. Male/female subject from 16 years of age or older. Subjects who are not legal adults may only be included where legally permitted and ethically accepted.
4. Subject for whom the Investigator believes a reasonable benefit from the long-term administration of BRV may be expected.
5. Female subjects without childbearing potential (postmenopausal for at least 2 years, bilateral oophorectomy or tubal ligation, complete hysterectomy) are eligible. Female subjects with childbearing potential are eligible if they use a medically accepted contraceptive method. Oral or depot contraceptive treatment with at least approved dosage of ethinylestradiol per intake in each country where this study is conducted (if subjects is taking any enzyme inducer such as carbamazepine, phenobarbital, primidone, phenytoin, oxcarbazepine, St. John's Wort or rifampicin, the dosage of ethinylestradiol should have been modified according to the guidelines for contraceptive treatment in each country), monogamous relationship with vasectomized partner, or barrier contraception are acceptable methods. The subject must understand the consequences and potential risks of inadequately protected sexual activity, be educated about and understand the proper use of contraceptive methods,

and undertake to inform the Investigator of any potential change in status. Abstinence will be considered as an acceptable method of contraception if the Investigator can document that the subject agrees to be compliant.

6. Subject/legally representative considered as reliable and capable of adhering to the protocol (eg, able to understand and complete diaries and questionnaires), visit schedule, or medication intake according to the judgment of the Investigator.

6.1.2 Additional inclusion criteria for rollover subjects

In addition to the inclusion criteria for all subjects in Japan (Section 6.1.1), the following criteria must also be met for rollover subjects in Japan:

3. Subject completed the Treatment Period and Transition Period of EP0083 or is ongoing in N01379 sites in Japan.

6.1.3 Additional inclusion criteria for directly enrolled subjects

In addition to the inclusion criteria for all subjects in Japan (Section 6.1.1), the following criteria must also be met for directly enrolled subjects in Japan:

7. Subject has a body weight $\geq 40\text{kg}$ at the Screening Visit (SV).
8. Subject has well-characterized focal epilepsy/epileptic syndrome according to the 1989 ILAE classification.
9. Subject has had an electroencephalogram (EEG) reading compatible with the clinical diagnosis of focal epilepsy within the last 10 years. If there is no appropriate EEG available within the last 10 years, a Baseline EEG must be scheduled at the SV and the results received before the EV.
10. Subject has 1 to <8 partial seizures (according to the 1981 ILAE classification) during the 8 weeks prior to BRV administration.
11. Subject's seizures are uncontrolled while treated by at least 1 permitted concomitant AED. Vagal nerve stimulation (VNS) will be allowed and counted as a concomitant AED.

6.1.4 Exclusion criteria for all subjects

Subjects in Japan are not permitted to enroll in the study if any of the following criteria is met:

1. Subject has developed hypersensitivity to any components of the IMP or comparative drugs as stated in this protocol during the course of the core study.
2. Severe medical, neurological or psychiatric disorders, or laboratory values which may have an impact on the safety of the subject.
4. Planned participation in any other clinical study of another investigational drug or device during this study.
5. Pregnant or lactating woman.
6. Any medical condition which, in the Investigator's opinion, warrants exclusion.

6.1.5 Additional exclusion criteria for rollover subjects

In addition to the exclusion criteria for all subjects in Japan (Section 6.1.4), the following exclusion criteria also apply for rollover subjects in Japan:

3. Poor compliance with the visit schedule or medication intake in the previous BRV studies.
7. Subject has a lifetime history of suicide attempt (including an active attempt, interrupted attempt, or aborted attempt), or has suicidal ideation in the past 6 months as indicated by a positive response ("Yes") to either Question 4 or Question 5 of the C-SSRS at the Entry Visit (EV).
8. Subject has $>2\times$ ULN of any of the following at the EV: ALT, AST, ALP, or $>$ ULN total bilirubin ($\geq 1.5\times$ ULN total bilirubin if known Gilbert's syndrome).
If subject has elevations only in total bilirubin that are $>$ ULN and $<1.5\times$ ULN, fractionate bilirubin to identify possible undiagnosed Gilbert's syndrome (ie, direct bilirubin $<35\%$).

6.1.6 Additional exclusion criteria for directly enrolled subjects

In addition to the exclusion criteria for all subjects in Japan (Section 6.1.4), the following exclusion criteria also apply for directly enrolled subjects in Japan:

9. Subject has participated in another study of an investigational medication (or a medical device) within the last 30 days or is currently participating in another study of an investigational medication (or a medical device).
10. Subject has a lifetime history of suicide attempt (including an active attempt, interrupted attempt, or aborted attempt), or has suicidal ideation in the past 6 months as indicated by a positive response ("Yes") to either Question 4 or Question 5 of the C-SSRS at the SV.
11. Subject has $>2\times$ ULN of any of the following at the SV: ALT, AST, ALP, or $>$ ULN total bilirubin ($\geq 1.5\times$ ULN total bilirubin if known Gilbert's syndrome).
If subject has elevations only in total bilirubin that are $>$ ULN and $<1.5\times$ ULN, fractionate bilirubin to identify possible undiagnosed Gilbert's syndrome (ie, direct bilirubin $<35\%$).
For subjects with a Baseline result $>$ ULN for ALT, AST, ALP, or total bilirubin, a Baseline diagnosis and/or the cause of any clinically meaningful elevation must be understood and recorded in the electronic Case Report form (eCRF).
12. Subject has $>$ ULN ALT, AST, or ALP that does not meet the exclusion limit at screening, repeat the tests, if possible, prior to dosing to ensure there is no further ongoing clinically relevant increase. In case of a clinically relevant increase, inclusion of the subject must be discussed with the Medical Monitor.
13. Subject previously enrolled in this study or any other prior study with BRV as a dosing arm.
14. Subject has experienced febrile seizures exclusively. The occurrence of febrile seizures in addition to other unprovoked seizures is not exclusionary.
15. Subject has a history or presence of status epilepticus during the 30 days preceding the SV.

16. Subject has a history or presence of known psychogenic nonepileptic seizures.
17. Study participant has been treated with vigabatrin and has visual field defects.
18. Subject is taking any drug that significantly influences the metabolism of BRV (cytochrome P450 strong inducers such as rifampin/rifampicin) except if the dose has been kept stable at least 4 weeks before the SV.
19. Subject has presence of any sign (clinical or imaging techniques) suggesting rapidly progressing (ie, not expected to stay stable during study participation) brain disorder or brain tumor per investigator assessment. Stable arteriovenous malformations, meningiomas, or other benign tumors may be acceptable.
20. Subject has any clinical conditions (eg, bone marrow suppression, severe renal impairment) which, per investigator discretion, impair reliable participation in the study or necessitate the use of medication not allowed by protocol.
21. Subject has the presence of a terminal illness.
22. Subject has the presence of a serious infection.
23. Subject has clinically significant laboratory abnormality that may increase the risk associated with study participation or may interfere with the interpretation of study results, according to the Investigator.
24. Subject has clinically significant ECG abnormalities according to the Investigator.
25. Subject has known alcohol or drug addiction or abuse within the last 2 years.

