^c If no appropriate EEG result (within the last 10 years) is available, the EEG must be scheduled at the SV and the results received before the EV.

^d A neuro-imaging procedure (brain magnetic resonance imaging/brain computerized tomography scan or any other imaging test) should be performed if no report is available within the previous 2 years. If there is not a known history and clinical signs or suspicion of brain tumor, performing a neuro-imaging procedure for the purpose of the study is not mandatory. If the investigator can judge a participant's eligibility by his/her own medical judgement without performing neuro-imaging procedure, it is also acceptable. However, if the etiology of epilepsy is a brain tumor, or the participant has any intracranial structural abnormality as documented by a previous neuro-imaging procedure, the participant needs to have documentation of a neuro-imaging procedure which is no older than 2 years.

^e At the SV and EV (For DE), historical seizure information (including type, frequency, and date) should be checked. Historical seizure information must have been prospectively recorded on a subject's own document (eg, DRC). After the EV, seizure counts are collected on the subject's DRC on a daily basis

^f Laboratory safety assessment will not be performed at MEV. Only liver function tests will be performed at the MEV in Visit 4 (M3) and Visit 6 (M9). Laboratory safety assessment is mandatory at the FV, except if the FV follows an EDV where laboratory results were normal. The result of the calculated creatinine clearance will be provided by the central laboratory.

^g At the SV, a serum pregnancy test will be performed for female subjects with childbearing potential. At all subsequent visits, a urine pregnancy test will be performed

^h Concomitant levetiracetam is permitted for directly enrolled subjects in Japan, but not allowed for subjects transitioning from EP0083 and N01379.

Table 5-2: Schedule of study assessments for subjects directly enrolled into EP0085 in Japan

Assessments	SV	EV	MEV	FEV	YEV	End of Study Visit or EDV	FV
Visit	V0	V1	V2, V4, V6, V8, V10...	V3, V5, V9...	V7, V11...	NA	NA
Month	-	M0	M1, M3, M9, M15, M21...	M2, M6, M18...	M12, M24...	NA	NA
Week	(-2 to -21 days)	W0	W4, W12, W36, W60, W84...	W8, W24, W72...	W48, W96...	NA	NA

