6.3 Withdrawal criteria

Subjects are free to withdraw from the study at any time, without prejudice to their continued care.

Subjects should be withdrawn from the study if any of the following events occur:

- Withdrawal for safety reasons by the Investigator such as a worsening of the seizure profile, eg, occurrence of status epilepticus, seizure clustering or generalized tonic-clonic seizure, if unknown for the subject

- Subject develops an illness that would interfere with his/her continued participation.
- Subject is noncompliant with the study procedures or medications in the opinion of the Investigator.
- Subject takes prohibited concomitant medications as defined in this protocol.
- Subject or legal guardian withdraws his/her consent.
- There is confirmation of a pregnancy during the study, as evidenced by a positive pregnancy test.
- The sponsor or a regulatory agency requests withdrawal of the subject.
- In the event of a suicide attempt, the subject should be referred immediately to a Mental Healthcare Professional and must be withdrawn from the study.

Subject has active suicidal ideation without specific plan as indicated by a positive response (“Yes”) to Question 4 of the “Since Last Visit” version of the C-SSRS. The subject should be referred immediately to a Mental Healthcare Professional and may be withdrawn from the study based upon the Investigator’s judgment of benefit/risk of continuing the subject in the study/on study medication.

Subject has active suicidal ideation with a specific plan as indicated by a positive response (“Yes”) to Question 5 of the “Since Last Visit” version of the C-SSRS. The subject should be referred immediately to a Mental Healthcare Professional and must be withdrawn from the study.

Investigators should attempt to obtain information on subjects, in the case of withdrawal or discontinuation. The Investigator should make effort (at least 1 phone call and 1 written message to the subject) and document his/her effort (date and summary of the phone call and copy of the written message in the source documents), to complete the final evaluation. All results of these evaluations and observations, together with a narrative description of the reason(s) for removing the subject, must be recorded in the source documents. The eCRF must document the primary reason for withdrawal or discontinuation.

Investigators should contact the Medical Monitor, whenever possible, to discuss the withdrawal of a subject in advance.

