7.2 Treatments to be administered

Directly enrolled subjects in Japan and subjects rolling over from EP0083 will be started on a BRV dose of 100mg/day (2 equally divided doses administered twice daily) at study entry and should be maintained at this dose for at least 2 weeks, unless the subject is not able to tolerate treatment.

Subjects from Japan who entered from N01379 can enter EP0085 at a dose up to 200mg/day. The BRV dose can be adjusted based on the individual subject's seizure control and tolerability between 50mg/day and 200mg/day during the study and must always be administered in equal morning and evening doses except the last week of down-titration. Of note, decreasing the dose should not exceed 50mg/day.

For all subjects, the first intake of study medication should occur in the evening of the day of the EV. Subjects should take tablets according to instructions provided by the Investigator.

During the Down-Titration Period, the BRV dose may be decreased in steps of a maximum of 50mg/day on a weekly basis. A last down-titration step at 25mg/day for 1 week should be included prior to the 2-week Study Drug-Free Period. The subject will be required to enter a 2-week Study Drug-Free Period for 2 weeks, followed by a FV.

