8.1 Screening Visit (for direct enrollers in Japan only)

The following tasks and procedures are to be performed between Day -21 and Day -2, prior to Visit 1 (EV) for direct enrollers in Japan:

- Written informed consent
- Subject identification card dispensed
- Eligibility assessment
- Demography
- Medical/procedures history
- Epilepsy history
- AED history
- Birth control
- Vital signs
- Body weight
- Height
- Physical examination
- Neurological examination
- 12-lead ECG
- EEG (if no EEG result within the previous 10 years is available)
- Neuro-imaging procedure (per Investigator discretion)
- IVRS/IWRS
- Seizure counts (prospectively recorded historical seizure information)
- Laboratory safety assessments including hematology, blood chemistry, and urinalysis
- Serum pregnancy test
- AE reporting
- C-SSRS
- Medical procedures
- Concomitant AEDs
- Concomitant non-AEDs

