8.2 Entry Visit (for direct enrollers in Japan only)

The EV assessments for direct enrollers in Japan are as follows:

- Eligibility assessment
- Vital signs
- Body weight
- IVRS/IWRS

- Subject's daily record card (DRC) dispensed
- Seizure counts (prospectively recorded historical seizure information)
- Laboratory safety assessments including hematology, blood chemistry, urinalysis and urine pregnancy test (if applicable)
- AE reporting
- C-SSRS
- Medical procedures
- Concomitant AEDs
- Concomitant non-AEDs
- Study drug dispensing

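### For direct enrollers in Japan, a new C-SSRS Question 4 'Yes' at the Entry Visit, hours before the first dose, is not an automatic exclusion, although the same answer at screening is

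*Protocol*

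**What the plan says.** Criterion 10 in Protocol Section 6.1.6 has two limbs for direct enrollers. One is a lifetime history of suicide attempt, with no visit attached. The other is ideation in the past 6 months, shown by a positive answer "to either Question 4 or Question 5 of the C-SSRS at the SV".

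Section 8.1 places the screening procedures so that they "are to be performed between Day -21 and Day -2, prior to Visit 1 (EV) for direct enrollers in Japan". Section 8.2 opens with "The EV assessments for direct enrollers in Japan are as follows", and its list includes both an eligibility assessment and the C-SSRS; Table 5-2 agrees. Under Section 7.2, "the first intake of study medication should occur in the evening of the day of the EV".

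Once a subject is in the study, Section 6.3 grades the response to the 'Since Last Visit' version of the C-SSRS. After a Question 4 'Yes', the subject "should be referred immediately to a Mental Healthcare Professional and may be withdrawn from the study", and the decision rests on the Investigator's "judgment of benefit/risk of continuing the subject in the study/on study medication". After a Question 5 'Yes' or a suicide attempt, withdrawal is mandatory.

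SAP Section 2.3 describes direct-enroller eligibility as confirmed at the SV.

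**The concern.** The protocol collects a fresh C-SSRS answer on the day of first dosing, alongside an eligibility assessment, but gives that answer no fixed eligibility consequence for Question 4. A subject who was negative at the SV and reports active ideation at the EV can start brivaracetam that evening if the investigator so decides. The same answer 2 to 21 days earlier, when it was less current, would have kept the subject out whatever the investigator thought.

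What is at stake is subject protection at the point of first exposure, and consistent application of an entry rule across sites. No efficacy or safety analysis depends on it: under SAP Section 9.3.7 the C-SSRS is listed only and is not a study variable.

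**Working it through.** The plan states no figure to reproduce, so the check is mainly a comparison of texts.

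**1. Which reading criterion 10 uses.** The visit qualifier attaches to the ideation limb, so only the SV reading counts. The EV eligibility assessment applies the criteria as written, and this one names the SV.

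**2. What happens to a new positive answer at the EV (direct enrollers):**

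| EV finding | Rule that applies | Consequence |
|---|---|---|
| Suicide attempt | Criterion 10, attempt limb (no visit named); Section 6.3 | Excluded, or must be withdrawn |
| Question 5 'Yes', 'Since Last Visit' version | Section 6.3 | Must be withdrawn |
| Question 4 'Yes', 'Since Last Visit' version | Section 6.3 | Referral; withdrawal discretionary |
| Question 4 or 5 'Yes', another version | No specific rule | General criteria only |

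The last row is needed because the protocol does not say which C-SSRS version is given at this visit. Section 10.3.6 mentions baseline/selection use and on-study use without assigning the EV to either.

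**3. Whether a general criterion closes the Question 4 gap.** Four could be invoked at the EV, and each rests on judgment:
- Inclusion 4 (Section 6.1.1): the investigator expects reasonable benefit from long-term treatment.
- Exclusion 2 (Section 6.1.4): the disorder is severe and may affect safety.
- Exclusion 6 (Section 6.1.4): the investigator considers that a medical condition warrants exclusion.
- Exclusion 20 (Section 6.1.6): a condition impairs reliable participation or requires disallowed medication, at the investigator's discretion.

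None is triggered by the C-SSRS answer itself.

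**4. Size of the exposed group.** Section 5.1.2 plans 30 direct enrollers, 127 subjects in Japan and 217 overall.
- Share of all subjects: 30/217 = 13.8%.
- Share of Japan: 30/127 = 23.6%.
- Gap between the two C-SSRS readings: 2 to 21 days, from the Day -21 to Day -2 window.

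**5. Expected number of cases.** The documents give no rate, so p, the probability that an SV-negative direct enroller answers 'Yes' to Question 4 at the EV, is an assumption. Expected cases = 30p; chance of at least one = 1 − (1 − p)^30, treating subjects as independent.

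| Assumed p | Expected cases | Chance of at least one |
|---|---|---|
| 0.5% | 30 × 0.005 = 0.15 | 1 − 0.860 = 14.0% |
| 1% | 30 × 0.01 = 0.30 | 1 − 0.740 = 26.0% |
| 3% | 30 × 0.03 = 0.90 | 1 − 0.401 = 59.9% |

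The expected count stays below one across the range. The 59.9% comes only from its upper end and should not be quoted alone.

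**The case against.** The strongest reply is that the protocol handles Question 4 by judgment on purpose. Section 6.3 separates it from Question 5 and from attempts. Protocol Amendment 4 revised these suicidality rules, made withdrawal after an attempt mandatory, and left Question 4 discretionary. Anchoring at screening is also a pattern in this cohort: body weight (inclusion 7) and exclusions 10, 11, 15 and 18 all refer to the SV. Where the protocol does address change between screening and dosing, for liver enzymes in exclusion 12, it asks for repeat tests if possible and a discussion with the Medical Monitor, not automatic exclusion. Finally, to dose a subject after a new Question 4 'Yes', an investigator would have to look past the four general criteria above and, where Section 6.3 applies, an immediate referral.

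Much of this stands, and it keeps the point small. It does not remove it. The Section 6.3 discretion concerns continuing someone in the study or on study medication, and a direct enroller at the EV has taken none. Before any dose, criterion 10 itself treats the answer as an absolute bar, so the graded approach is not the protocol's own pre-dose standard.

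Two broader readings may tempt a reader, and neither is supported.

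- *That the protocol's treatment of seizure counts shows safety screens in this cohort should run up to dosing.* Inclusion 10 counts seizures "during the 8 weeks prior to BRV administration", and Table 5-2, footnote e, says: "At the SV and EV (For DE), historical seizure information (including type, frequency, and date) should be checked". That window is also the efficacy baseline, fixed at 56 days in SAP Sections 3.3 and 8.1.2, so it has its own reason to end at dosing.
- *That exclusion 15, status epilepticus in the 30 days before the SV, leaves a comparable gap.* Section 6.3 and exclusion 2 largely cover a new episode. Any remainder depends on one reading of an ambiguous qualifier in a list that is only illustrative.

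The rollover criteria do name the EV for the same C-SSRS questions, but rollovers have no SV, and their C-SSRS comes from the last visit of the previous study. That is not a precedent.

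**Conclusion.** The point holds for Question 4 at the EV in direct enrollers. The wording leaves a gap of 2 to 21 days, ending on the day of first dosing, in which a new positive answer moves from automatic exclusion to investigator discretion. It concerns about 30 of 217 planned subjects, with fewer than one case expected under an assumed 0.5% to 3% rate that has no source in the documents.

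A reader might infer that suicidal subjects can enter unchecked. The documents do not support that: attempts are covered, Question 5 on the 'Since Last Visit' version requires withdrawal, and a Question 4 'Yes' on that version requires referral. The conclusion that Question 5 is covered assumes that this version is the one given at the EV.

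This is a cheap improvement, at the level of something to consider.

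**What to change.** In Section 6.1.6, criterion 10, replace *at the SV* with *at the SV or the EV (whichever C-SSRS version is administered)*. The bracket matters because the EV version is not specified. Leave the Section 6.3 discretion for Question 4 during treatment as it is, and leave criterion 15 unchanged.

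The cost is a few words in one criterion. No visit, assessment or analysis is added, since the C-SSRS and the eligibility assessment are already scheduled at the EV. The downside is an occasional late screen failure: 0.15 to 0.9 expected among 30 subjects under the assumed rates.

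The documents do not say whether direct enrollment has closed. If it has, the C-SSRS listings planned in SAP Section 9.3.7 can be checked for a Question 4 'Yes' at the EV, and the wording kept for any later direct-enrollment cohort.
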